7.3. Trial completion and post-trial therapy

The trial for a patient will be considered completed after the 6th visit on the 90th day after thrombolysis.

7.4. Criteria for early termination of trial participants

A patient should be withdrawn from the trial immediately after any of the following situations occur:

- a patient or his/her legal representative or attending physician sends a request to exclude the patient from the trial, based on the withdrawal of Informed Consent (the patient's unwillingness to continue participation in the trial);
- pregnancy;
- significant violation of the Protocol procedures;

The reason for each unscheduled termination should be noted in the Case Report Form (CRF) in the section "Trial Completion". Follow-up will be performed for all patients who have dropped out of the trial due to adverse events or other safety parameters.

Follow-up will also be performed for all patients who have dropped out of the trial for other reasons, but also experience adverse events or have other safety parameters that might lead to discontinuation of therapy. In the case of early termination, the treatment of the underlying disease continues in accordance with recommendations and health standards.

Follow-up should be continued until the patient's condition is restored; until the diagnosis of an adverse event or a change in the safety parameter is stabilized or established chronically; as long as there are clinical indications for follow-up, or the duration of follow-up is determined by an attending physician-investigator.

In the case of pregnancy, every effort should be made to fully monitor the course of pregnancy until the moment of delivery, and child growth.

Randomized patients who did not complete the trial for reasons including those related to the trial drug will be included in the analysis of efficacy and safety data. Replacement of the removed randomized patients with newly included ones is not provided.

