Trial duration:	The trial completion date is the 90th day after the final trial patient was included in the trial. All patients will be examined for 90 days
Trial population:	Men and women aged 18 years and older with a diagnosis of ischemic stroke no later than 4.5 hours after the onset of symptoms.
Sample size:	The total number of patients included in the trial – 336 people, including 10 % of possible dropouts
Study drug:	
Fortelyzin®, registration number – 001941 as of December 18, 2012.
 
Pharmaceutical form: Lyophilizate for preparation of a solution for intravenous administration, 5 mg (745,000 IU), supplied with a solvent
 
Composition:
 
Active substance: Forteplase® (recombinant protein containing the amino acid sequence of staphylokinase) 5 mg (745,000 IU).
 
Excipients: L-arginine - 15,0 mg, L-histidine – 2,0 mg, glycine – 30,0 mg, povidone-17: 20,0 mg, polysorbate-20: 0,4 mg.
 
Solvent: 5 mL ampule of sodium chloride 0.9%, solution for injection

Inclusion criteria:	
 • Men and women aged 18-80 (inclusive) years old. • Verified diagnosis of ischemic stroke (neuroimaging (CT/MRI) signs of ischemic stroke, from 5 to 25 points on the NIHSS scale). • Duration of symptoms of ischemic stroke is not more than 4.5 hours before starting thrombolytic therapy. • The patient's consent to use reliable contraceptive methods throughout the trial and within 3 weeks after: 
 – women who have a negative pregnancy test and use the following means of contraception: intrauterine devices, oral contraceptives, a contraceptive patch, long-acting injectable contraceptives, a double-barrier method of contraception. Women who are not at risk of pregnancy for health-related reasons (documented conditions: hysterectomy, tubal ligation, infertility, menopause for more than 1 year) may also be involved in the trial); – men who use barrier contraception. Men who unable to fertilize (documented conditions: vasectomy, infertility) may also be involved in the trial. • A participant provided signed and dated informed consent of participation in the trial.

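### Section 7.4 takes patients out of the trial for an undefined protocol violation and secures no day-90 mRS afterwards, yet counts them in the efficacy analysis

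*Combined protocol and SAP*

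**What the plan says.** Section 7.4 opens with "A patient should be withdrawn from the trial immediately after any of the following situations occur". The triggers are withdrawal of consent, pregnancy, and a "significant violation of the Protocol procedures". The exit is from the trial, not only from treatment. Nothing in the document defines a significant violation or says who decides that one has occurred.

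For patients who have left, section 7.4 promises follow-up in limited circumstances:

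- Those who left because of adverse events or other safety parameters are followed.
- For the rest: "Follow-up will also be performed for all patients who have dropped out of the trial for other reasons, but also experience adverse events" or have comparable safety findings.
- Pregnancies are monitored to delivery and beyond.

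Safety follow-up runs until the condition resolves or stabilises, or while clinically indicated, or "the duration of follow-up is determined by an attending physician-investigator". No mRS assessment and no day-90 contact is required.

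The section then states that randomised patients who did not complete the trial "will be included in the analysis of efficacy and safety data", and that "Replacement of the removed randomized patients with newly included ones is not provided".

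Elsewhere, section 7.3 says "The trial for a patient will be considered completed after the 6th visit on the 90th day after thrombolysis". Section 9 and Table 5 in section 8 place the day-90 mRS at that visit. The protocol summary says "All patients will be examined for 90 days", and section 8 makes similar general statements.

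**The concern.** The primary endpoint is mRS 0–1 at day 90, and all-cause mortality at day 90 is a safety endpoint. A patient withdrawn on day 3 for a violation, with no adverse event, has no stated route to either assessment but must still be analysed. The protocol itself creates this missing outcome, so it is avoidable.

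Two features make it more than a clerical gap. First, withdrawal for a violation rests on judgement, and that judgement is made with the arm known. The regimens differ (a bolus of seconds against a bolus plus an infusion of up to an hour), so the loss could differ by arm, although nothing in the document says that it would. Second, this is a non-inferiority comparison, where counting missing outcomes as failures can pull the arms together and make a worse drug look acceptable. Section 18 names no analysis set and no rule for a missing day-90 mRS, so the handling is open as well.

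**Working it through.** **Textual check.** Take a patient withdrawn for a violation and apply the sections in order.

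1. Section 7.4: the patient leaves the trial at once.
2. Section 7.4: without an adverse event, safety finding or pregnancy, no further follow-up is promised. With one, follow-up ends with the event or on the physician's decision.
3. Sections 7.3, 8 and 9: day-90 mRS is taken at Visit 6, which this patient no longer attends.
4. Section 7.4: the patient is nevertheless in the efficacy analysis.

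Steps 3 and 4 are compatible only if someone collects the outcome outside the stated rules.

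**The plan's own figure.** Section 17 assumes 54.8% response in both arms, a 16-point margin, two-sided 5% (one-sided 2.5%) and 80% power:

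n = (1.960 + 0.842)² × 2 × 0.548 × 0.452 / 0.16² = 151.9, so 152 per arm. This agrees with the protocol. Then 152 × 1.10 = 167.2, so 168 per arm.

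**Illustration of size.** The plan gives no violation rate; the 10% in section 17 is dropout from all causes. The loss fractions and the response rates of those lost are therefore assumptions.

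The true rates are set at the non-inferiority boundary: Actilyse 0.548, Fortelyzin 0.548 − 0.16 = 0.388, n = 168 per arm. The unpooled standard error is √(0.388 × 0.612/168 + 0.548 × 0.452/168) = 5.37 points.

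Type I error = Φ((p_F,obs − p_A,obs + 0.16)/SE − 1.96)

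Let f be the share of an arm lost and q the true response rate of those lost.

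- Missing counted as failure: p_obs = p − f·q, with n = 168.
- Completers only: p_obs = (p − f·q)/(1 − f), with n = 168(1 − f).

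No loss gives 2.50%. *Worked case:* 5% lost from Actilyse only, q = 0.40, counted as failures. p_A,obs = 0.548 − 0.05 × 0.40 = 0.528; difference = 0.388 − 0.528 = −0.140; SE = 5.38 points; Φ(0.020/0.0538 − 1.96) = 5.6%.

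Type I error when all the loss is in one arm (q = 0.2 / 0.3 / 0.4):

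| Arm losing patients | Handling | 1% lost (about 2 patients) | 5% lost (about 8 patients) |
|---|---|---|---|
| Actilyse | failures | 2.73 / 2.84 / 2.97% | 3.80 / 4.64 / 5.61% |
| Actilyse | completers | 2.14 / 2.24 / 2.34% | 1.08 / 1.39 / 1.77% |
| Fortelyzin | failures | 2.29 / 2.19 / 2.10% | 1.59 / 1.25 / 0.98% |
| Fortelyzin | completers | 2.71 / 2.60 / 2.49% | 3.77 / 3.04 / 2.43% |

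The largest shift in the estimated difference is f × q: 0.01 × 0.40 = 0.4 points at 1%, and 0.05 × 0.40 = 2.0 points at 5%.

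The completers bias in the losing arm is f(p − q)/(1 − f). It is zero when those lost respond at that arm's own rate (0.548 for Actilyse, 0.388 for Fortelyzin at the boundary) and changes sign above it. For Fortelyzin with q = 0.548 and f = 0.05 it is −0.84 points, and the type I error is 1.72%.

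**Equal random loss counted as failure.** The true −16 points shrinks to −16 × (1 − f): −15.2 at 5% loss (type I error 3.5%) and −14.4 at 10% (about 4.8%). A completers analysis stays at 2.5%.

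Simulation of 1,000,000 trials per case supports the approximation: 2.3% with no loss; 3.7% and 5.5% for 5% Actilyse-only loss as failures (q = 0.2 and 0.4); 3.5% and 5.0% for equal loss of 5% and 10%.

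**The case against.** The strongest reply is that no bias has been shown. The violation rate is unknown, and the one-arm cases assume both the split and the prognosis. At 5% loss, 7 of the 12 cases in the table are conservative and 5 inflated; at 1% the effect is negligible. All of that stands, and it is why the figures serve only to show scale. The equal-loss figures depend on a missing-data rule that section 18 does not state, and they would follow from any dropout. That stands too, so they support only the secondary point about section 18.

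A second reply is that the summary and section 8 commit to 90 days for patients generally, and that including non-completers in the analysis presupposes their outcomes are sought. But section 7.4 is the specific rule for patients who leave, and no sentence says that they still attend Visit 6. If that is the intention, it should be written down.

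A third reply is that adverse events are defined so broadly (section 12), and followed to completion, that many stroke patients would be followed anyway. This narrows the group left with no follow-up at all. It does not close the gap, because following an event to resolution does not produce an mRS at day 90.

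Finally, early exit might be thought to protect the patient. Once dosing is complete, within about an hour by section 10, leaving for a violation spares no study-drug exposure. This argument does not cover violations found before or during dosing.

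**Conclusion.** The concern holds. It rests on the text: section 7.4 removes patients from the trial for an undefined reason, secures no day-90 mRS or vital status for them, and still requires them in the efficacy analysis. The general 90-day statements do not override it.

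The consequence cannot be quantified from the document. Under the stated assumptions, a 5% loss confined to one arm moves the nominal 2.5% type I error to between 1.0% and 5.6%, and a 1% loss to between 2.1% and 3.0%. The direction depends on which arm loses patients, on their prognosis and on how missing outcomes are handled. Against a 16-point margin and a standard error of about 5.4 points, this matters mainly for a result near the margin. The change should be made because the loss is avoidable and cheap to prevent; the plan has not been shown to be biased.

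**What to change.** Amend section 7.4 so that:

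- a protocol violation is recorded as a deviation and does not end follow-up;
- the patient stays in the schedule to Visit 6;
- day-90 mRS and vital status are collected for every randomised patient unless consent to follow-up itself is withdrawn;
- all randomised patients are analysed in their assigned arm.

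Align the 90-day statements in the summary and section 8 with this wording.

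As a secondary change, add a sentence to section 18 on how any day-90 mRS still missing is handled, noting that counting it as failure is not a conservative choice for non-inferiority.

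The cost is wording in section 7.4, one sentence in section 18 and a few extra day-90 contacts. The visit is already planned for every patient, and the sample size does not change.

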8. DESIGN AND PLAN OF RESEARCH ACTIVITIES

The current trial is a multicenter, open-label, randomized, parallel-group, phase III b non-inferiority trial to compare the efficacy and safety of the trial drug.

The trial will include 336 patients with ischemic stroke. The patients will be monitored for 90 days: 1-2 days in the Neurological Intensive Care Unit and the Department of Neurology in the remaining days before discharge (on average 14 days), with an outpatient visit on the 90th day.

Start of research, initiation of centers: «_____» 20___

Enrollment of patients: «_____» 20___

Result processing and reporting: «_____» 20___

The enrollment period may be extended to total patient enrollment if a research center fails to enroll the planned number of patients. The end date of the trial is considered to be the end date of the trial in all patients involved.

In each research center, the subject of the trial is assigned a serial number that corresponds to the sequence of patient inclusion in the trial. The serial number is reflected in the Case Report Form (CRF). The list of patient's identification is stored in the trial file. Patients are included in the trial only after signing the Informed Consent Form.

Before the trial, all patients will undergo the following procedures: collection of thorough medical history, measurement of vital signs, physical examination, assessment of neurological status, CT/MRI scans of the brain, duplex scanning, and angiography of the brain vessels (if necessary), ECG, blood and urine samples for laboratory tests:

***complete blood count:** hemoglobin, red blood cells, hematocrit, leukocyte formula: neutrophils, eosinophils, basophils, monocytes, lymphocytes, platelets, ESR;

***biochemical blood parameters:** total protein, creatinine, urea, AST, ALT, CK, total bilirubin, glucose, sodium, potassium, cholesterol, HDL-C, triglycerides;

***coagulogram:** fibrinogen, activated partial thromboplastin time (aPTT), INR, prothrombin;

***common urine analysis:** color, transparency, reaction, density, glucose, protein, bilirubin/urobilinogen, white blood cells, red blood cells.

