17. CALCULATION OF SAMPLE SIZE

No multicenter randomized clinical trials of thrombolytic therapy in ischemic stroke have been conducted in the Russian Federation before. Available scientific literature is related to the pilot application of Actilyse® in a limited number of AIS patients (10-16 people) (V. I. Skvortsova et al., 2006, N. A. Shamalov, 2015). Thus, the data of the SITS-MOST international register and the results of randomized multicenter clinical trials of Actilyse® in comparison with placebo in patients with ischemic stroke were used as the basis for the sample size justification.

The calculation of the number required was carried out taking into account the capacity of 80 % and planning of a non-inferiority study in parallel groups [V. I. Sergienko, I.B. Bondareva "Mathematical statistics in clinical trials"; GEOTAR-Media, Moscow, 2006]. The null hypothesis (H_0) was that the thrombolytic therapy with Fortelyzin® is worse than the standard thrombolytic therapy with Actilyse®. This means that frequency of the primary efficacy criterion in the comparison group (P_{Actilyse}) is higher than in the group of the study drug ($P_{\text{Fortelyzin}}$), taking into account the "no worse" boundary (δ):

$$H_0: P_{\text{Fortelyzin}} - P_{\text{Actilyse}} \leq -\delta$$

The alternative hypothesis (HA) is that Fortelyzin® therapy is no less effective than the standard thrombolytic therapy with Actilyse:

$$H_A: P_{\text{Fortelyzin}} - P_{\text{Actilyse}} > -\delta$$

The calculation of the sample size for the "no worse" hypothesis, the primary criterion representing the proportion of respondents, and even 1:1 distribution in therapy groups is carried out according to the following formula [Chow S-Ch., Shao J., Wang H., "Sample Size Calculations in Clinical Research", 2003]:

$$n = \frac{(z_{1-\alpha} + z_{1-\beta})^2}{(\delta - \Delta)^2} [p_1(1 - p_1) + p_2(1 - p_2)]$$

where n – the number of patients in each of the groups compared;

p_1 – the proportion of **respondents** (reaching the primary efficacy criterion) in the group of the study drug;

p_2 – the proportion of **respondents** in the comparison group with Actilyse®;

$\Delta = p_1 - p_2$ – the expected difference between the proportions of respondents in the groups of the study drug and the comparison drug;

δ – “no worse” boundary

α and β – probabilities of type I and II errors, respectively;

$Z_{1-\alpha}$ and $Z_{1-\beta}$ – critical values of the standard normal distribution.

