The limit of clinical significance was chosen to be 16.9% and was calculated as follows.

The frequency of reaching the primary efficacy criterion in the thrombolytic therapy of ischemic stroke using Actilyse®, namely, the percentage of good functional recovery 3 months after thrombolysis (MRS – 0-1 score) according to the International Register (SITS-MOST) is 54.8 % (total number of patients is 6 483) (Wahlgren N et al., SITS-MOST investigators. Multivariable analysis of outcome predictors and adjustment of main outcome results to baseline data profile in randomized controlled trials; Safe Implementation of Thrombolysis in Stroke Monitoring Study (SITS-MOST). *Stroke* 2008; 39: 3316-3322).

The frequency of reaching the primary efficacy criterion when using placebo – the percentage of good functional recovery (MRS-0-1 score) in patients with ischemic stroke 3 months after thrombolysis, is on average 37.9%. This value was obtained according to the ECASS II, Atlantis, and ECASS III studies, where the favorable effect when using placebo was 36.6%, 32 %, and 45.2%, respectively (Hacke W et al, for the Second European-Australasian Acute Stroke Study Investigators. Randomized double-blind placebo-controlled trial of thrombolytic therapy with intravenous alteplase in acute ischaemic stroke (ECASS II. *Lancet* 1998;352:1245-1251),

(Clark W.M., et al., for the Atlantis Study Investigators. for the Second European-Australasian Acute Stroke Study Investigators. Recombinant tissue-type plasminogen activator for ischemic stroke 3 to 5 hours after symptom onset. The Atlantis Study: A Randomized Controlled Trial. *JAMA* 1999;282:2019—26),

(Hacke W, et al. "Thrombolysis with Alteplase 3 to 4.5 Hours after Acute

Ischemic Stroke". ECASS III The New England Journal of Medicine. 2008. 359(13):1317-1329).

Thus, the difference between a good clinical recovery in patients with AIS with the use of Actilyse® and placebo is $54,8\% - 37,9\% = 16,9\%$. Thus, the "no worse" boundary was set as 16%.

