Assuming equal proportions of reaching the primary efficacy criterion in the study drug group and the comparison drug group of 54.8% ($\Delta = 0$), with the established "no worse" boundary of 16% and demonstration at the bilateral significance level of 5%, the minimum number of patients included in the trial is estimated as 152 people in each therapeutic group to maintain 80% of the comparison power. Taking into account the possible 10% dropout, it is recommended to increase the sample size to 336 patients (168 patients in each group).

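### Non-completers and protocol violators stay in the non-inferiority analysis, but the plan gives no rule for a missing day-90 mRS and no per-protocol analysis

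*Combined protocol and SAP*

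**What the plan says.** Section 8 describes a "phase III b non-inferiority trial to compare the efficacy and safety of the trial drug". The primary endpoint (Section 11) is mRS 0-1 on day 90, which is Visit 6, and Section 7.3 counts a patient as complete only after that visit.

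Section 7.4 lists the reasons for withdrawal: consent withdrawn, pregnancy, or a significant violation of protocol procedures. It then says "Randomized patients who did not complete the trial for reasons including those related to the trial drug will be included in the analysis of efficacy". The same sentence covers the safety analysis, and withdrawn patients are not replaced. It promises follow-up after dropout where there are adverse events or safety findings. It does not say that a day-90 mRS will be obtained from patients who leave for other reasons.

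Section 17 sets the margin ("boundary was set as 16"%) and the dropout allowance: "Taking into account the possible 10% dropout, it is recommended to increase the sample size to 336 patients", that is, 168 per arm.

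Section 18 is the whole statistical section. It names tests and regression models. It names no analysis set, no rule for a missing day-90 mRS, no per-protocol or sensitivity analysis, and no confidence-limit rule for declaring non-inferiority.

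**The concern.** A patient who leaves without a day-90 mRS can enter a responder proportion only if an outcome is assigned, and the plan does not say which. If the same outcome, or the same success rate, is assigned in both arms, a real deficit of the test drug looks smaller than it is. Protocol deviators whose outcome does not depend on the assigned drug act in the same way. In a superiority trial that shrinkage is cautious; in a non-inferiority trial it favours the claim. No second analysis is planned that would show whether the conclusion depends on these patients. Because the trial is open-label and the rule is unwritten, the choice could be made when allocation and outcomes are already known. At stake is a false conclusion of non-inferiority on the primary endpoint.

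**Working it through.** **Inputs from Section 17.** Level: "demonstration at the bilateral significance level of 5"%, used as one-sided 2.5%. Power: "to maintain 80% of the comparison power". Rates: "Assuming equal proportions of reaching the primary efficacy criterion in the study drug group and the comparison drug group of 54.8"%. Margin: 16 points. Allocation: "even 1:1 distribution in therapy groups". Dropout: 10%; 168 per arm.

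**Assumptions, not in the documents.** Non-inferiority is declared when the lower limit of the two-sided 95% interval for the risk difference is above -16 points (unpooled standard error). The outcome assigned to dropouts is varied below.

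**1. The plan's own figure.** n = (1.960 + 0.842)² × 2 × 0.548 × 0.452 / 0.16² = 151.9, so 152 per arm, as stated. A one-sided 5% level would give 120, so one-sided 2.5% is the level in use. With dropout, 152 × 1.1 = 167.2, so 168.

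**2. False-positive rate at the boundary.** Take a true control rate of 54.8% and a true test rate of 38.8%. With dropout fractions d_T and d_C and assigned success rate r:

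- p_T* = (1 - d_T) × 0.388 + d_T × r
- p_C* = (1 - d_C) × 0.548 + d_C × r
- SE = √{[p_T*(1 - p_T*) + p_C*(1 - p_C*)] / 168}
- error = Φ[(p_T* - p_C* + 0.16)/SE - 1.96]

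With equal dropout d the difference is -0.16 × (1 - d), whatever r is.

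For 10% in each arm, counted as failure (r = 0): p_T* = 0.3492, p_C* = 0.4932, difference -0.144, SE = 0.0533. The error is Φ(0.016/0.0533 - 1.96) = Φ(-1.66) = 4.85%.

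| Handling of non-completers (test/control dropout) | Difference, points | Normal approximation | Exact binomial |
|---|---|---|---|
| True day-90 outcome, or own arm's rate | -16.0 | 2.50% | 2.36% |
| Failure, 5%/5% | -15.2 | 3.51% | 3.55% |
| Failure, 10%/10% | -14.4 | 4.85% | 5.00% |
| Failure, 15%/15% | -13.6 | 6.60% | 6.68% |
| Common rate 46.8%, 10%/10% | -14.4 | 4.82% | 4.59% |
| Common rate 54.8%, 10%/10% | -14.4 | 4.81% | 4.49% |
| Failure, 8%/12% | -12.5 | 9.51% | 9.80% |
| Failure, 5%/15% | -9.7 | 21.56% | 22.18% |
| Failure, 12%/8% | -16.3 | 2.22% | 2.29% |
| Failure, 15%/5% | -19.1 | 0.55% | 0.57% |

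The common-rate rows also describe deviators who share one outcome rate in both arms.

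**3. Completers only.** 168 × 0.9 gives about 151 per arm. If dropout is unrelated to outcome, the error is 2.5% (exact 2.6%). Now suppose control dropout is random, but in the test arm 15% of non-responders and 2% of responders drop out (about 10% overall). The test rate among completers is 0.388 × 0.98 / (0.388 × 0.98 + 0.612 × 0.85) = 0.422. The difference is -12.6 points, SE = 0.0571, and the error is Φ(0.0343/0.0571 - 1.96) = 8.7%.

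**4. Power.** Simulated with equal true rates of 54.8% and 10% missing: 82.7% for all randomised with missing counted as failure, 79.9% for completers, and about 78% if both must succeed.

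**The case against.** The strongest reply is that retaining non-completers is not what causes the inflation. Fortelyzin is a single bolus and Actilyse is given within about an hour (Section 10), so a later dropout has already been treated. With true day-90 outcomes, or imputation at the arm's own rate, the error stays at 2.5%. A reader might infer that Section 7.4 in itself pulls the arms together, or that the planned 10% dropout doubles the error. The documents do not support that: they state no scoring rule, and the result depends on the rule and on the balance of dropout. This part of the reply stands in full.

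Counting failure is also right for some non-completers. A patient who dies before day 90 has a known non-response, and if every non-completer were a true failure that scoring would leave the error at 2.5%. This stands too, and is why deaths need separating from unknown outcomes.

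Nor is a per-protocol or completers set a safe harbour, since step 3 gives 8.7% under informative dropout. A reader might infer that success in both sets must be mandatory. Within-arm imputation already removes the inflation when the recorded scores explain the missingness, so a formal double hurdle is a design choice.

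Finally, a reader might see a conflict between Section 17's dropout inflation and Section 7.4. Going from 152 to 168 is an ordinary power allowance and defines no analysis set.

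What the reply does not supply is the missing rule. Nothing in Sections 7.4 or 18 rules out common scoring, and no analysis without the deviators is planned.

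**Conclusion.** The point holds as a gap in specification. Non-completers, including patients withdrawn for significant violations, are kept in the efficacy analysis of a non-inferiority trial with no missing-outcome rule and no per-protocol analysis. If they are scored alike in both arms, 10% per arm turns a true -16-point difference into about -14.4 and raises the one-sided error from about 2.5% to about 5%. With unequal dropout averaging 10% and counted as failure, the error is about 10% at 8%/12% (test/control) and about 2.3% at 12%/8%. These figures assume a true difference exactly at the margin, 168 per arm, dropout unrelated to outcome within arm, and a decision on the two-sided 95% interval. They are scenarios, not a prediction. The change is worth making because it is cheap and settles the choice before outcomes are known.

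**What to change.** In Sections 7.4 and 18:

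1. Make the primary non-inferiority analysis all randomised patients by assigned arm. Count deaths before day 90 as non-response. Multiply impute any other missing day-90 mRS within arm, from the mRS, NIHSS and Barthel scores that the visit schedule already collects up to day 14. Do not set it to a common value.
2. Pre-specify a per-protocol analysis by written rule (eligible, received the allocated drug, day-90 mRS observed or died), against the same -16-point limit.
3. Require any disagreement between the two to be reported and to qualify the non-inferiority conclusion.

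The cost is wording and one more analysis, with no extra patients. Within-arm imputation relies on the recorded scores explaining the missingness. If the sponsor chose to require success in both sets formally, joint power would be about 78% at 10% dropout (simulated with missing counted as failure in the all-randomised set), against the planned 80%.
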